9.4. Programming Conventions

- Page orientation, margins, and fonts: Summary tables, listings, and figures will appear in landscape orientation. There should be a 1.0" boundary on the left and right edges. The top and bottom margins are 1.0" for tables and listings, but may vary for figures. Output should be printed in Courier New with a point size of 8.
- Identification of analysis population: Every summary table, listing, and figure will clearly specify the analysis population being summarized/listed. Listings will be prepared for all subjects randomized.
- Group headers: In the summary tables, the group headers will identify the within-group sample size for the indicated analysis population. Of note, the header's sample size does not necessarily equal the number of subjects actually summarized within any given summary module; some subjects in the analysis population may have missing values and thus may not be summarized.
- Suppression of percentages corresponding to null categories: When count data are presented as category frequencies and corresponding percentages, the percent should be suppressed when the count is zero in order to draw attention to the non-zero counts.
- Presentation of sample sizes: Summary modules should indicate, in one way or another, the number of subjects actually contributing to the summary statistics presented in any given summary module. As mentioned above, this may be less than the number of subjects in the analysis population.
 - ◆ In the quantitative modules describing continuous variables (and thus presenting sample size, means, and standard deviations), the sample size should be the number of non-missing observations
 - ◆ For categorical variables that are presented in frequency tables, the module should present the total count in addition to the count in each category. Percentages should be calculated using this total as the denominator, and the percentage corresponding to the sum itself (that is, 100%) should be presented so as to indicate clearly to a reviewer the method of calculation.
- Sorting: Listings will be sorted by treatment, subject number and date, if applicable. If a listing is sorted in a different manner, it will be indicated on the listing shells.
- General formatting rules: Rounding for all variables will occur only as the last step, immediately prior to presentation in listings, tables, and figures. No intermediate rounding will be performed on derived variables. The standard rounding practice of rounding numbers ending in 0-4 down and numbers ending in 5-9 up will be employed.
- The presentation of numerical values will adhere to the following guidelines (exceptions may be necessary in some circumstances for derived analysis variables to allow readability):
 - ◆ Raw measurements will be reported to the number of significant digits as captured electronically or on the eCRFs.

- ◆ Standard deviations will be reported to two decimal places beyond the number of decimal places the original parameter is presented. EQ-5D-5L Index Score summaries will use 4 decimal places for standard deviation.
- ◆ Means medians, and quartiles will be reported to one decimal place beyond the number of decimal places the original parameter is presented.
- ◆ will be reported to the one decimal place beyond the number of decimal places the original parameter is presented.
- ◆ Calculated percentages will be reported with one decimal place.
- ◆ Coefficient of variation will be reported to the same number of decimal places as the standard deviation.
- ◆ P-values will be reported to 4 decimal places
- Dates will be formatted as DDMMYY. Partial dates will be presented on data listings as recorded on eCRFs.
- Time will be presented according to the 24-hour clock (HH:MM).
- Verification of Results: All analyses will be subject to formal verification procedures. Specifically, results will be verified utilizing independent programming prior to issuance of the draft statistical report. All documents will be verified by the lead statistician to ensure accuracy and consistency of analyses.

9.6. Core Codes for imputation of MAR and MNAR

9.6.1. Imputation of Missing at Random (MAR) Cases

SAS PROC MI will be used to generate 27 possible imputed datasets using the following SAS code:

```
proc mi data=mcmc1 seed=SEED1 nimpute=27 out=Out1X;
mcmc chain=multiple displayinit initial=em(itprint);
var TRT y0 y1 y2 ... yn;
run;
```

Here, TRT is an indicator variable representing treatment with values of 'CVL-751 5 mg', 'CVL-751 15 mg', or 'Placebo', Y₁ - Y_N represent the response variable (e.g., MDS-UPDRS Part II+III score) for each visit, Y₀ is the baseline score, and SEED1 is a random number.

Each of these datasets will be analyzed using PROC MIXED in SAS using the MMRM model. The results of the analyses of the datasets will be combined using PROC MIANALYZE to produce an inferential result.

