5.5. Strata and Covariates

The randomization is stratified by concurrent use of MAO-B inhibitor. This factor is planned to be included as a covariate in the efficacy analyses. However, due to isolated administrative errors at a few sites during randomization through IRT system, 15 subjects were randomized to the incorrect strata (3 non-MAO-B inhibitor users were randomized to the MAO-B inhibitor use stratum and 12 MAO-B inhibitor users were randomized to the non-user stratum; details in [Section 9.7](#)). The actual MAO-B inhibitor use status, as recorded in eCRF, will be used as a covariate instead of the randomization strata in these cases.

The baseline value of each efficacy variable (if applicable) will also be included as a covariate in the efficacy analyses.

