5.9.2. Main Analytical Approach

The change from baseline to each study visit in MDS-UPDRS Part II and III combined score will be summarized by visit and treatment group. A mixed model repeated measures (MMRM) analysis will be used to analyze the data from all post-randomization timepoints up to Week 27 with fixed effect of treatment group, visits, interaction between treatment group and visit, and baseline MAO-B inhibitor use. The baseline value of MDS-UPDRS Part II and III combined score will also be included as a covariate. Subject will be included as a random effect. An unstructured covariance structure will be used for the repeated measures. If the unstructured covariance matrix results in convergence issue, the heterogeneous Toeplitz covariance structure followed by the heterogeneous first-order autoregressive (AR(1)) structure will be used. The Kenward-Roger approximation will be used to estimate the denominator degrees of freedom. The difference between each active dose and placebo at the endpoint visit (Week 26) will be estimated based on the Least Squares Mean (LSMean) difference derived from the MMRM with the associated 95% confidence intervals (CI) and P-values. A Cohen's D value will also be derived as the ratio of the estimated difference to the population standard deviation at each visit estimated from the model (the square root of the diagonal elements of the estimated covariance matrix). The missing values, including missing due to missed visits or early termination due to COVID-19 control measures, are assumed to be missing at random (MAR) in the main MMRM analysis. Sensitivity analyses will be performed to assess the impact of deviation from MAR assumptions on the analysis results. Time curve plots will be presented for both raw Mean (SEM) and LSMean (SE).

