5.9.3.4. Impact of Missing Values Handling

Whilst every effort will be made to prevent avoidable missing values during the study conduct ([National Research Council, 2010](#)), it is unrealistic to expect no missing values in clinical trials. The impact of missing values on the analysis results will be assessed by the sensitivity analyses described below.

Under Missing at Random (MAR) Assumption

Multiple imputation (MI) will be performed to replace each missing value with a set of plausible values that represent the uncertainty about the correct value to impute. The Markov chain (MCMC) method will be utilized for the mITT set. SAS PROC MI will be used to generate 27 possible imputed datasets: Each of these datasets will be analyzed using PROC MIXED in SAS using the MMRM model as described in [Section 5.9.2](#). The results of the analyses of the datasets will be combined using PROC MIANALYZE to produce an inferential result.

Considerations of Data Potentially Missing Not at Random (MNAR)

A pattern mixture model (PMM) approach will be used to address potentially MNAR patterns. The following three patterns of subjects in the mITT set will be considered:

- 1) Subjects with no missing values from discontinuation or from initiation of prohibited Parkinson's disease concomitant mediation during treatment period.
- 2) Subjects with missing values from the types of ICEs below will be considered having MNAR
 - a. Subjects who discontinue due to reasons, as recorded on the eCRF, of lack of efficacy, adverse events associated with motor symptoms of Parkinson's disease, physician decision, and withdrawal by subject.
 - b. Subjects who initiated concomitant Parkinson's disease medications (ATC classifications of ADAMANTANE DERIVATIVES, DOPAMINE AGONISTS, MONOAMINE OXIDASE B INHIBITORS, OTHER ANTI-PARKINSON DRUGS, OTHER DOPAMINERGIC AGENTS, or DOPA AND DOPA DERIVATIVES) after the first dose of IMP and prior to the last dose of IMP with a use duration of 7 days or more will be considered having a potential confounding ICE. The efficacy data post ICE will be treated as missing with the missing pattern of MNAR.

The MNAR cases will be identified and documented prior to database lock and unblinding ([Section 9.5](#)).

- 3) Subjects with missing values from the type of ICEs below will be considered as having MAR

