 - a. Missing values after discontinuation due to reasons, as recorded on the eCRF, of death, pregnancy, loss to follow-up, adverse event unrelated to motor symptoms of Parkinson's disease, non-compliance, site termination, protocol deviation, failure to meet continuation criteria and other will be considered as MAR.

The MNAR pattern 2) above in the active treatment group will be imputed using the jump to reference (J2R) method (Cro et. al. 2020) by assuming that patients jump to behave like those in the placebo group following their last observed time point. However, such MNAR in the placebo group will still be imputed as MAR using the standard multiple imputation method.

The MAR patterns 3) will be imputed using the standard multiple imputation method described above.

Other missing values due to missed visits/assessments before endpoint or discontinuation will also be assumed as MAR and imputed using the standard multiple imputation method for all three patterns.

Core codes for MAR and MNAR imputations are provided in [Section 9.6](#).

Under Missing Completely at Random (MCAR) Assumption

An additional sensitivity analysis will be conducted on the Endpoint (Week 26) Completer set using the MMRM analysis method described in [Section 5.9.2](#).

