9.6.2. Imputation of Missing Not at Random (MNAR) Cases

The MNAR cases are imputed using reference based imputation (J2R) method. The five macros; SAS code for reference based multiple imputation [<https://www.lshtm.ac.uk/research/centres-projects-groups/missing-data#dia-working-group>] will be used to generate 27 possible imputed datasets using the following sample SAS code:

```
%include "&Path\part1A_33.sas";
%include "&Path\part1B_47.sas";
%include "&Path\part2A_40.sas";
%include "&Path\part2B_31.sas";
%include "&Path\part3_55.sas";
%include "&Path\plotter_7.sas";

%part1a(Jobname=X, Data=XX, Subject=usubjid, Response=aval, Time=avisitn, Treat=Trt01pn, cov=BASE, Catcov=MAOBINHI, covgroup=trt01pn, Debug=1);
%part1b(Jobname=X, Ndraws=27, thin=350, seed=s, Debug=1);

%part2a(Jobname=X_J2R, inname=XX, method=J2R, ref=0, Debug=1);
%part2b(Jobname=X_J2R, seed=s, Debug=1);
```

Each of these datasets will be analyzed using PROC MIXED in SAS using the MMRM model. The results of the analyses of the datasets will be combined using PROC MIANALYZE to produce an inferential result.

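### The missing-at-random imputation code leaves out MAO-B inhibitor use, which the model fitted to the imputed data and the jump-to-reference code both include (minor, free to fix)

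*SAP*

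**What the plan says.** SAP 5.5 names the factor and its role: "The randomization is stratified by concurrent use of MAO-B inhibitor. This factor is planned to be included as a covariate in the efficacy analyses". The same section uses actual use from the eCRF for the 15 subjects randomized in the wrong stratum.

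The primary MMRM in SAP 5.9.2 has fixed effects that include "interaction between treatment group and visit, and baseline MAO-B inhibitor use", with the baseline score as a covariate.

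SAP 5.9.3.4 plans two imputation-based checks.

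- Multiple imputation under MAR. After imputation, "Each of these datasets will be analyzed using PROC MIXED in SAS using the MMRM model", that is, the model with MAO-B use.
- A pattern-mixture analysis. Active-arm pattern 2 cases are imputed by jump to reference (J2R). Pattern 2 cases on placebo go to the MAR method, as do missed visits in any pattern. For the rest, "The MAR patterns 3) will be imputed using the standard multiple imputation method described above".

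The code for the MAR method is in SAP 9.6.1. It opens with "proc mi data=mcmc1 seed=SEED1 nimpute=27 out=Out1X" and lists its variables as "var TRT y0 y1 y2 ... yn". The legend defines only treatment, the baseline score, the visit scores and the seed. There is no MAO-B term and no BY statement. The J2R code in SAP 9.6.2 has "cov=BASE, Catcov=MAOBINHI, covgroup=trt01pn".

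**The concern.** An imputation model should contain at least the covariates of the model fitted afterwards. Here it lacks one, and that one is the stratification factor. For a subject with missing data, MAO-B use then influences the imputed value only through the scores already observed. Imputed users are drawn toward non-users and the reverse.

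There are two consequences. The MAR check should differ from the primary analysis in method alone, but it also drops a conditioning variable, so any gap between the two results could not be cleanly explained. Within the pattern-mixture analysis, the conditioning set differs by arm for the same kind of event: active pattern 2 cases are imputed with MAO-B use and placebo pattern 2 cases without it.

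A link between MAO-B use and missingness is plausible from the plan itself. Under SAP 5.9.1, starting an MAO-B inhibitor on treatment for 7 days or more censors later data. Protocol inclusion criterion 10 requires existing users to keep a stable dose, so that route is open mainly to non-users. The same two checks are repeated for the Part II key secondary endpoint (SAP 5.10.1.2).

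**Working it through.** **Which step conditions on MAO-B use**

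| Step | MAO-B use in the model? |
|---|---|
| Primary MMRM (5.9.2) | yes |
| MAR multiple imputation, all missing values (9.6.1) | no |
| Pattern mixture: active pattern 2 (9.6.2) | yes |
| Pattern mixture: placebo pattern 2, pattern 3, intermittent gaps (9.6.1) | no |
| MMRM fitted to the imputed data | yes |

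**Setting for the size check.** SAP 1.2 gives 174 per group, 4 points, SD 9, two-sided alpha 0.025, 90% power and 27% dropout. With n = 2(z₀.₉₈₇₅ + z₀.₉₀)²(9/4)² = 2(2.241 + 1.282)² × 5.0625 ≈ 126, the t-test version is 127, and 127/0.73 = 174. The SAP figure reproduces. This point does not turn on it.

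**Approximate formula.** Let γ be the MAO-B outcome difference at the endpoint and q the proportion of users among subjects still observed in an arm. If no visit scores helped the imputation, and MAO-B use is balanced at baseline, the shift in the dose-placebo difference would be γ(q_active − q_placebo). It is zero when the dropout link is the same in both arms. As an example, take 30% users, with placebo dropout of 15% in non-users and 35% in users, and the reverse on active:

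- q_placebo = 0.30×0.65 / (0.30×0.65 + 0.70×0.85) = 0.195/0.790 = 0.247
- q_active = 0.30×0.85 / (0.30×0.85 + 0.70×0.65) = 0.255/0.710 = 0.359
- difference = 0.112, so the shift is 0.17 points for γ = 1.5, 0.34 for γ = 3 and 0.56 for γ = 5.

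This is a rough ceiling, because baseline and earlier visit scores carry part of γ. A simulation of such patterns (300,000 subjects, 8 visits) gave 0.04 to 0.18 points for γ of 1.5 to 3, and up to 0.27 for γ = 5.

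**Independent simulation.** Three arms, 8 post-baseline visits, SD 9 at the last visit, true effect −4, about 27% dropout in the main scenarios, and treatment entered as two dummy variables so that only the MAO-B omission varies. Normal imputation was run with and without MAO-B use. The last visit was then analysed by ANCOVA on treatment, baseline and MAO-B use, as a stand-in for the MMRM. The table gives the large-sample change in the treatment estimate (without minus with MAO-B), at 100,000 per arm.

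| Users | MAO-B effect | Dropout link equal in all arms | Users' dropout 15% placebo, 45% active | 10% placebo, 60% active |
|---|---|---|---|---|
| 20% | 0 | 0.02 | −0.01 | 0.01 |
| 20% | −2 | 0.00 | 0.13 | 0.13 |
| 20% | −4 | −0.01 | 0.12 | 0.25 |
| 20% | +4 | 0.02 | −0.13 | −0.28 |
| 40% | 0 | 0.01 | −0.02 | 0.03 |
| 40% | −2 | −0.01 | 0.19 | 0.22 |
| 40% | −4 | 0.01 | 0.24 | 0.42 |
| 40% | +4 | 0.02 | −0.24 | −0.41 |

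The rows with zero effect show simulation error of up to 0.03, so the equal-link column cannot be told from zero.

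At 174 per arm with 27 imputations, 30% users and an effect of −4, the mean paired shift is 0.01 (equal link) or 0.17 (15% against 45%). The standard error is about 1.05 either way, so 0.17/1.05 = 0.16 standard errors. The extreme case is 0.42/1.05 = 0.40.

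**The case against.** The strongest reply is that this is code tidying. Any visible shift needs MAO-B use to predict outcome and to relate to dropout differently by arm, and nothing in the documents suggests that pattern. Randomization is stratified on MAO-B use, and the imputation model holds baseline and every visit score. Only supportive analyses are touched. The PGIC endpoint has no multiple-imputation analysis (SAP 5.10.2.2). All of this stands, and it is why the point is minor.

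One could also call the 9.6.1 block illustrative, with the final program free to add the term. That is weaker. The block is complete, its legend lists every variable, 5.9.3.4 names no further imputation covariates, and the neighbouring block does include MAO-B use.

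Three stronger readings are tempting and not supported.

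- A reader might infer that the whole pattern-mixture check ignores MAO-B use. It does not: the active-arm J2R step, which carries the departure from MAR, includes it.
- A reader might describe MAR without MAO-B use as a weaker assumption. It is a different condition and generally a less plausible one; when MAO-B use predicts both missingness and outcome, it demands more, not less.
- A reader might infer that the primary result is at risk. The primary MMRM conditions on MAO-B use and uses no imputation.

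**Conclusion.** The omission is real and unexplained: the MAR imputation model is narrower than both the model fitted to its output and the J2R imputation model. It affects the MAR multiple-imputation check and the MAR-imputed parts of the pattern-mixture check, for the primary and Part II endpoints. The likely shift in the dose-placebo difference is about 0.00 to 0.02 points. It reaches about 0.1 to 0.4 points, in either direction, only if MAO-B use predicts outcome and its link to dropout differs by arm.

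Those figures rest on assumed prevalence (20% to 40%), outcome effects (up to 4 points) and dropout by stratum, and on a last-visit ANCOVA with monotone dropout in place of the full MMRM. None of the scenarios would by itself be expected to reverse a conclusion on a 4-point effect. The case for acting is consistency at no cost, not the size of the bias.

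**What to change.** Add the 0/1 MAO-B use variable to the VAR statement in SAP 9.6.1, taking actual use from the eCRF as SAP 5.5 prescribes. It is a fully observed baseline item that the MMRM already needs, so it can serve as a predictor in the MCMC step. Add one sentence to 5.9.3.4 saying that MAR imputation conditions on MAO-B use.

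The cost is one variable name and one sentence, ideally before database lock and unblinding. If the SAP is already closed, record the change in the study report as SAP 6 provides.

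This brings in the MAO-B covariate used in 5.9.2 and 9.6.2. It does not make the two code blocks identical, since the `covgroup` setting in 9.6.2 has no counterpart in 9.6.1. How TRT, a single variable with three text values, enters the same statement is a separate point that this change does not settle.

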5.2. Populations for Analyses

The analysis populations are defined [Table 4](#).

Table 4: Populations for Analysis

Population	Description	Analysis
ITT	All randomized subjects	Demographic and Baseline Characteristics
FAS	All randomized subjects who receive at least 1 dose of IMP. This will be the safety analysis set.	Safety analysis
mITT	All randomized subjects who receive at least 1 dose of IMP and have a baseline and at least one postbaseline MDS-UPDRS assessment.	Primary analysis set for efficacy
Endpoint completers	All subjects in the mITT population who have an MDS-UPDRS assessment at baseline and endpoint	Sensitivity analysis set for efficacy
PK	All randomized subjects who receive at least 1 dose of tavapadon and have at least one measurable scheduled tavapadon (CVL751) concentration	PK analysis set

Abbreviations: FAS = full analysis set, IMP = investigational medicinal product, ITT = intent-to-treat, mITT = modified intent-to-treat, PK = pharmacokinetic, MDS-UPDRS = Movement Disorder Society – Unified Parkinson’s Disease Rating Scale.

[figure not shown]

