5.10.1.2. Sensitivity Analyses

The sensitivity analyses described in [Section 5.9.3](#) for the primary estimand will also be performed for the secondary efficacy estimand 1.

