5.10.2.2. Sensitivity Analyses

The sensitivity analyses described in [Section 5.9.3](#) for the primary estimand will also be performed for the secondary efficacy estimand 2 except for the sensitivity analyses to assess the impact of missing value handling. For the secondary efficacy estimand 2, the case of potential MNAR will be imputed as “non-responder” for the sensitivity analysis. No additional sensitivity analysis under the MAR assumption using multiple imputations will be performed. In addition, a sensitivity analysis excluding the PGIC score obtained remotely may be performed if such remote assessments are conducted due to COVID-19 restrictions.

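### SAP 9.6.1 enters the three arms as one variable in the imputation model; coded as one number, it forces the arm means onto a line and can bias a dose contrast in the missing-data sensitivity analyses

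*SAP*

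**What the plan says.** SAP 5.9.3.4 plans a multiple-imputation sensitivity analysis under MAR: "The Markov chain (MCMC) method will be utilized for the mITT set". The three arms are therefore pooled. There are 27 imputed datasets, each analysed with the MMRM of SAP 5.9.2. SAP 5.2 defines mITT as "All randomized subjects who receive at least 1 dose of IMP and have a baseline and at least one postbaseline MDS-UPDRS assessment".

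SAP 9.6.1 gives the code. It says "TRT is an indicator variable representing treatment with values of" 5 mg, 15 mg and placebo, and lists the model variables as "var TRT y0 y1 y2 ... yn". There is no BY statement, no CLASS statement and no second treatment column. The SAP does not say how three text labels become numbers.

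The analysis model treats the arms separately (SAP 5.9.2): "The difference between each active dose and placebo at the endpoint visit (Week 26) will be estimated" from a model with a treatment-by-visit interaction.

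The same imputation step is used elsewhere:

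- In the pattern-mixture analysis, "The MAR patterns 3) will be imputed using the standard multiple imputation method described above". SAP 5.9.3.4 also uses it for placebo cases classed as MNAR and for intermittent gaps.
- For Part II, SAP 5.10.1.2 says the sensitivity analyses "for the primary estimand will also be performed for the secondary efficacy estimand 1".
- It is not used for PGIC responders (SAP 5.10.2.2): "No additional sensitivity analysis under the MAR assumption using multiple imputations will be performed".

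Jump-to-reference draws for the active arms use separate macros (SAP 9.6.2).

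**The concern.** A multivariate-normal model cannot use text labels, so TRT has to be recoded. Any single code with three distinct values makes the imputed mean at each visit linear in that code. The imputation model is then more restrictive than the analysis model it feeds, and imputed values in at least one arm are pulled towards the line.

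The MAR multiple imputation is there to check the MMRM under the same MAR assumption, so the two should agree closely. A single code would put a gap between them that comes only from the coding. The same pull, diluted, enters the pattern-mixture analysis.

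The primary and Part II MMRMs, the hierarchical tests of SAP 5.4, the active-arm jump-to-reference draws, the completer analysis and the PGIC analyses do not use this step and are not affected.

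**Working it through.** **1. Scale of the trial.** The documents give no figure for imputation bias, so the design figures set the scale. SAP 1.2 has a difference of 4, SD 9, two-sided alpha 0.025, 90% power and 27% dropout:

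n = 2 x 81 x (2.2414 + 1.2816)^2 / 16 = 125.7, so 126 evaluable; 126 / 0.73 = 172.6, so 173 per arm.

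The stated 174 reproduces: 174 x 0.73 = 127 evaluable, power 90.3%. Protocol 9.2 gives alpha 0.05 for the same 174, which has 94.3% power. That difference does not bear on this point.

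**2. The constraint.** With one code c, the imputation mean at visit j is a_j + b_j'(other scores) + g_j x c. Given the other scores, dose effects against placebo are therefore in the ratio of the code differences:

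- placebo/5/15 = 0/1/2: the 5 mg effect is forced to 1/2 of the 15 mg effect;
- 0/5/15: the 5 mg effect is forced to 1/3 of the 15 mg effect;
- listed order, 5 mg = 1, 15 mg = 2, placebo = 3: the 15 mg effect is forced to 1/2 of the 5 mg effect.

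The constraint acts on imputed values only. Earlier observed scores carry part of the true arm difference, so the bias is a fraction of the departure from the line.

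**3. Simulation inputs.**

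- From the documents: 174 per arm, visits at Weeks 5-27, SD of change 9, 27% dropout, 27 imputations, and removal of subjects with no postbaseline score. That leaves on average 489-502 of 522 subjects and 22-24% missing at Week 26.
- Assumed: baseline SD 12, baseline slope -0.15, effect rising linearly from Week 2 to Week 14 and then flat, monotone dropout independent of outcome (even, or 70% of it by Week 11), residual correlation exchangeable 0.4-0.8 or AR(1) 0.7-0.85.
- Placebo = 0 is also assumed. The only numeric treatment code in the SAP is the reference value 0 in SAP 9.6.2, and the reference there is placebo.
- Analysis: MMRM with Rubin's rules. Equal effects used 400 trials in each of 10 cells; other cases used 600 trials in each of 4 cells. Monte Carlo error of a shift is about 0.01. Not run in SAS.

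**4. Results at Week 26, Parts II+III, standard error 1.01-1.11.** Departure is the true 5 mg effect minus its value on the coded line.

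| True effects (5, 15 mg) | Departure, 0/1/2 | 5 mg shift, 0/1/2 | Departure, 0/5/15 | 5 mg shift, 0/5/15 |
|---|---|---|---|---|
| -4, -4 | -2 | shrinks 0.24-0.35 | -2.67 | shrinks 0.34-0.50 |
| -3, -4 | -1 | shrinks 0.12-0.15 | -1.67 | shrinks 0.22-0.26 |
| -2, -4 | 0 | 0.00-0.02 | -0.67 | shrinks 0.10-0.11 |
| -1, -4 | +1 | false gain 0.13-0.16 | +0.33 | false gain about 0.06 |
| 0, 0 | 0 | 0.01 or less | 0 | 0.01 or less |

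The shift is roughly 0.12-0.19 points per point of departure. With both doses at -4, 15 mg moves by 0.02 or less (0/1/2) or shrinks by 0.07-0.12 (0/5/15).

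Example, both doses at -4, exchangeable 0.6, even dropout, estimates for (5 mg, 15 mg):

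- MMRM on the incomplete data: (-3.90, -3.95)
- two indicators: (-3.90, -3.95)
- 0/1/2: (-3.65, -3.95)
- 0/5/15: (-3.54, -3.88)

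Rejection at 0.05 for 5 mg with both doses at -4: 95-99% with indicators, 94-98% with 0/1/2, 92-98% with 0/5/15.

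**5. Separate checks.**

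- A second simulation with 174 per arm and about 27% missing gave 5 mg estimates of -4.04 (indicators), -3.69 (0/1/2) and -3.54 (0/5/15). Listed-order coding gave 15 mg -3.72 against -4.07 with indicators.
- A large-sample check with the mITT exclusion and about 21% missing gave 5 mg -3.99, -3.78 and -3.64 for the same three options. Listed order gave 15 mg -3.75 with both doses at -4, and -3.63 with true effects (-2, -4).
- Without the mITT exclusion, the 5 mg shifts of step 4 at (-4, -4) rise to 0.28-0.41 (0/1/2) and 0.41-0.59 (0/5/15). The size therefore depends on how much is missing; the direction does not.

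**6. Pattern-mixture analysis.** Both doses at -4, with half of active-arm dropouts assumed to go to jump-to-reference: 5 mg shrinks by 0.17-0.20 and 15 mg by 0.04-0.05 (0/1/2), or 0.25-0.29 and 0.11-0.13 (0/5/15).

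**7. Part II.** No SD is given, so it was not simulated. Since the shift is proportional to the departure, equal dose effects with the same correlation and dropout would shrink the 5 mg effect by 0.24/4 to 0.35/4, that is 6-9% (0/1/2), or 0.34/4 to 0.50/4, that is 8.5-12.5% (0/5/15).

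**The case against.** The SAP shows a gap in the coding, not a proven bias. It calls TRT an indicator and gives it text values, so the printed step cannot run on those labels without a recoding the SAP leaves out. If that recoding is two 0/1 columns, the problem disappears. This stands as a condition. But the text defines one variable with three values and the list names one variable, so a programmer following it could well use one number. Independent programming to the same specification would not necessarily catch this.

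The placebo = 0 code is borrowed from a different variable in a different step. That also stands. Which dose suffers cannot be known from the documents, and the listed order would put the loss on 15 mg, the first comparison in the hierarchy.

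Equal effects lie far from the coded line. Protocol 4.3 hints at graded effects, for which the shifts are smaller and can be nil. That evidence is thin: a small flexible-dose trial with 26 tavapadon subjects in maintenance, judged on Part III.

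Finally, only sensitivity analyses are involved and significance hardly moves. This is correct and limits the weight of the point. It does not remove it, because the purpose of the MAR run is to agree or disagree with the MMRM for reasons other than coding.

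**Conclusion.** The concern holds. As written, SAP 9.6.1 allows, and most literally describes, an imputation model that ties the two dose effects together while the analysis model leaves them free. With both doses at -4 and placebo coded 0, the loss in the 5 mg contrast is 0.24-0.50 points across the two codings, about a quarter to just under half of a standard error. Rejection falls by at most about 3 percentage points. Graded effects give smaller shifts, and equal means in all arms give none. With listed-order coding the loss falls on 15 mg instead.

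These sizes rest on the assumed correlation, effect build-up, dropout timing and coding. The direction follows from the algebra. The change should be made, but the primary conclusion does not depend on it.

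**What to change.** In SAP 9.6.1, do one of the following and state it in the text:

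- impute separately by randomized arm (BY TRT, with TRT removed from the variable list); or
- replace TRT with two 0/1 indicators, one for 5 mg and one for 15 mg.

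In the simulations the two options agreed within 0.02 points, and two indicators matched the MMRM on the incomplete data within 0.01. The same wording should govern every use of this step: the MAR analysis, the MAR-imputed values of the pattern-mixture analysis, and both again for Part II. The cost is one or two lines of SAS code and one SAP sentence, before unblinding.
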